### **Virologic Resistance**

Pretreatment NS5A RAVs were observed in 26% to 29% of subjects across the treatment groups. The presence of pretreatment NS5A RAVs did not impact treatment outcome in the SOF/VEL+RBV 12 Week group. Slightly lower SVR rates were observed in subjects with genotype 1 HCV infection with NS5A RAVs treated with SOF/VEL for 12 or 24 weeks compared to subjects without pretreatment NS5A RAVs. No virologic failures were observed in subjects with genotype 2, 4, or 6 HCV infection. The small numbers of subjects with genotype 3 HCV infection with pretreatment NS5A RAVs precluded meaningful subgroup analysis. The presence of pretreatment NS5B RAVs did not impact treatment outcome in any treatment group.

The majority of subjects had NS5A RAVs present at virologic failure with Y93H being the most common variant. NS5B NI RAVs were less common and typically observed at low levels. Of the 9 subjects with genotype 1 HCV infection with virologic failure, 6 had NS5A RAVs at failure (5 treatment emergent and 1 maintained from pretreatment). Two genotype 1 HCV-infected subjects had L159F and S282T NS5B NI RAVs present at failure; both of these subjects had multiple NS5A RAVs at pretreatment that reduce susceptibility to VEL. All 13 subjects with genotype 3 HCV infection with virologic failure had Y93H at failure (10 were treatment emergent). Three genotype 3 HCV-infected subjects had low levels of NS5B NI RAVs emerge at virologic failure.

### **Safety Results**

Overall, treatment with SOF/VEL±RBV for 12 weeks or SOF/VEL for 24 weeks was generally safe and well tolerated. Adverse events were consistent with the expected clinical sequelae in the setting of decompensated cirrhosis and, in addition, with the known toxicities of RBV in the SOF/VEL+RBV 12 Week group.

A smaller percentage of subjects in the SOF/VEL 12 Week and SOF/VEL 24 Week groups experienced any AE (81.1% in each group) compared with the SOF/VEL+RBV 12 Week group (90.8%). The higher frequency of AEs observed in the SOF/VEL+RBV 12 Week group was primarily due to AEs consistent with RBV-associated toxicity. No treatment-related Grade 3 AEs were reported in > 1 subject in any group or overall.

Most AEs were Grade 1 (mild) or Grade 2 (moderate) in severity. Overall, the most commonly reported Grade 3 or 4 AEs were hepatic encephalopathy and sepsis (5 subjects each), which are consistent with the natural history of disease progression in a population with decompensated liver disease.

Serious adverse events (SAEs) occurred in 17.6% of subjects in similar proportions across treatment groups, and only 1 subject (0.4%) experienced SAEs considered related to SOF/VEL. The most commonly reported SAEs were hepatic encephalopathy and sepsis (5 subjects each). Nine deaths occurred during the study, 2 of which were treatment emergent, and none of which was assessed as related to study drugs. One subject in the SOF/VEL 24 Week group underwent a liver transplantation on Post-treatment Day 8 after completing 35 days of treatment.

Nine subjects discontinued all study drugs due to an AE (SOF/VEL 12 Week group: 1.1%, 1 subject; SOF/VEL+RBV 12 Week group: 4.6%, 4 subjects; SOF/VEL 24 Week group: 4.4%, 4 subjects). No AE leading to discontinuation of study drugs was reported in > 1 subject. A total of 31.0% (27 of 87) of subjects had modified or interrupted RBV dosing due to AEs, and 10.3% (9 of 87) of subjects permanently discontinued RBV due to AEs while continuing SOF/VEL.

The majority of subjects had at least 1 Grade 3 or 4 laboratory abnormality (42.7% and 12.4%, respectively) with the highest rates observed in the SOF/VEL+RBV group (Grade 3: 43.7%; Grade 4 18.4%) due to a higher rate of hematologic abnormalities. The most commonly observed Grade 3 or 4 hematology laboratory abnormalities were decreased lymphocytes, hemoglobin, and platelet counts, all of which are a known effect of RBV therapy or expected in a subject population with decompensated liver disease.

The most commonly observed Grade 3 or 4 chemistry laboratory abnormalities were increased glucose and increased total bilirubin. All of the Grade 3 or 4 increased glucose abnormalities occurred in subjects with a history of diabetes mellitus or had elevated glucose at baseline or continuing through the Post-treatment period. The majority of subjects with Grade 3 or 4 increased total bilirubin (71.7%, 22 of 31 subjects) were in the SOF/VEL+RBV 12 Week group, primarily in a pattern that was consistent with RBV-induced hemolysis.

No notable changes in vital signs (systolic blood pressure, diastolic blood pressure, and pulse) were reported during the study. No trends in electrocardiogram findings suggestive of cardiotoxicity were observed.

## Conclusions

The conclusions from this interim analysis were as follows:

- Treatment with SOF/VEL±RBV for 12 or 24 weeks in subjects with decompensated cirrhosis resulted in high SVR12 rates:
  - In the SOF/VEL 12 Week group, the SVR12 rate was 83.3% (75 of 90 subjects).
  - In the SOF/VEL+RBV 12 Week group, the SVR12 rate was 94.3% (82 of 87 subjects).
  - In the SOF/VEL 24 Week group, the SVR12 rate was 87.8% (79 of 90 subjects).

- The SVR12 rates were highest in subjects treated with SOF/VEL+RBV for 12 weeks with few virologic failures:
  - In subjects with genotype 1 HCV infection, the virologic failure rate was 1.5% (1 of 68 subjects).
  - In subjects with genotype 3 HCV infection, the virologic failure rate was 15.4% (2 of 13 subjects), of which 1 subject had on-treatment breakthrough with PK data showing undetectable plasma drug levels consistent with non-adherence to study drug.
- Overall, there were no virologic failures in subjects with genotype 2, 4, or 6 HCV infection.
- The SVR12 rates between the SOF/VEL 12- and 24-week treatment durations were similar across all genotypes.
- The presence of pretreatment NS5A and NS5B RAVs did not impact treatment outcome with SOF/VEL+RBV for 12 weeks.
- Approximately half of subjects who achieved SVR12 experienced an early improvement in CPT and MELD scores, primarily related to improvements in synthetic function (albumin) and decreases in bilirubin.
- SOF/VEL was generally well tolerated in these subjects with decompensated liver disease, as evidenced by low rates of study treatment discontinuation and the majority of Grade 3 and 4 AEs, SAEs, and laboratory abnormalities being consistent with clinical sequelae of advanced liver disease and RBV toxicity.

## 1.8. Rationale for This Study

This is a Phase 2 study designed to evaluate the efficacy and safety of the SOF/VEL tablet administered for 4 weeks to subjects starting in the perioperative period of liver transplantation.

After transplantation, recurrence of HCV infection occurs in almost all patients {Feray et al 1992}, {Wright et al 1992} who have HCV RNA detectable prior to transplantation. HCV recurrence is associated with cirrhosis, fibrosing cholestatic hepatitis, graft loss, liver re-transplantation, and death {Prieto et al 1999}, {Wiesner et al 2003}, {Berenguer et al 2002}, {Gane et al 2008}, {Crespo et al 2012}, {Charlton et al 2014}, {Berenguer et al 2000}, {Forman et al 2002}, {Firpi et al 2009}. HCV RNA levels fall significantly in the anhepatic phase of liver transplantation and continue to fall during the first 12-24 hours post transplantation. Serum HCV RNA then begin to rise rapidly from the second post-operative week and peak by the fourth month {Charlton 2003}.

Deposition of fibrotic tissue in most HCV transplanted livers is highly accelerated with the development of bridging fibrosis and cirrhosis in 20-54% at 5 years and 32-51% at 7 years {Berenguer et al 2013}. Once cirrhosis is established, the probability of liver graft failure is 42% within 12 months {Berenguer et al 2002}.

There is great advantage to administering a well-tolerated direct acting antiviral without the use of PEG-IFN or RBV in the immediate postoperative period while the HCV RNA virus is at its lowest level. We hypothesize that the time period prior to re-infection is unique and mimics that of acute infection, as the nidus of HCV chronic infection (pretransplant liver) has been removed. For this reason, we believe that a short course of therapy (eg, 4 weeks), is likely to be successful. If the progression of the HCV virus can be halted before the progressive liver fibrosis activity is initiated both the new graft and the patient stand a greater chance of survival.

Additionally, patients who start HCV treatment pre-transplant may not have time to complete the full duration of treatment when a liver becomes available. The results of this study can inform on the safety and efficacy of continuing SOF/VEL treatment through transplantation.

### **1.8.1. Rationale for the Dose of SOF/VEL**

Sofosbuvir 400 mg, once daily, when dosed in combination with RBV with or without Peg-IFN has demonstrated broad genotypic efficacy and favorable safety profile in over 1700 HCV-infected subjects across multiple patient populations in Phase 2 and 3 trials. This dose is the approved marketed dose of sofosbuvir for the treatment of HCV-infection and, as such, was selected for co-formulation with VEL into a fixed-dose combination tablet.

VEL 100 mg was administered in combination with SOF 400 mg for 12 weeks to 237 HCV-infected subjects in Phase 2 studies. VEL 100 mg was selected for co-formulation with SOF based on the Phase 2 safety, PK and antiviral activity (studies GS-US-342-0102, GS-US-342-0109, and GS-US-337-0122 [Cohort 4]). The Phase 1 study GS-US-281-0102 established the anti-HCV activity of VEL and indicated that the exposures achieved following administration of doses > 25 mg provide at least 80% of maximal antiviral response in all HCV genotypes. SOF/VEL (400 mg /100 mg) as a FDC tablet was evaluated in the phase 3 ASTRAL program.

The favorable safety and efficacy profiles of SOF 400 mg and VEL 100 mg support further evaluation of this combination and doses in clinical development.

### **1.9. Risk/Benefit Assessment for the Study**

The regimen to be assessed in this study combines a potent HCV nucleotide inhibitor with a potent HCV NS5A inhibitor in patients who are in the immediate post-transplant operative period. This study will provide information of the safety and efficacy of SOF/VEL, a potent HCV nucleotide inhibitor and a potent HCV NS5A inhibitor. This combination has the potential to be the first once-daily, PEG-free, RBV-free, pangenotypic regimen for the treatment of chronic HCV infection in patients who have received a liver transplant. The potential benefits of early treatment in the peritransplant period with SOF/VEL:

- The once-daily, single tablet, short duration, pangenotypic HCV regimen would offer a simple algorithm for patients infected with HCV undergoing liver transplants, regardless of genotype
- A short duration of therapy which should lead to better outcomes through improved adherence.

The safety profile of SOF in clinical studies includes over 1700 chronic HCV-infected subjects that have been administered  $\geq 12$  weeks of SOF and RBV+/-Peg-IFN. No clinical safety issues specifically related to SOF have been identified to date

The safety profile of SOF + VEL 25mg or VEL 100mg administered for 8 or 12 weeks has been established in over 800 patients in Phase 2 studies. The safety profile of the proposed therapeutic regimen of SOF 400 mg and VEL 100 mg administered for 12 weeks has been established in 237 subjects enrolled in Phase 2 studies. No clinical safety issues specifically related to VEL or SOF + VEL have been identified to date. No clinical safety issues specifically related to the NS5A inhibitor class including daclatasvir (DCV) and LDV have been identified to date {[Afdhal et al 2014a](#)}, {[Afdhal et al 2014b](#)}, {[Kowdley et al 2014](#)}.

The safety profile of SOF/VEL has been studied in 4 Phase 3 trials (ASTRAL 1-4) in 1302 patients. Twelve weeks of SOF/VEL was generally well tolerated, and lead to a similar incidence of AEs and SAEs compared to placebo in patients with GT 1, 2, 4, 5, or 6 HCV (See Section 1.2.2.1). When 12 weeks of SOF/VEL was compared to SOF + RBV for 12 weeks in patients with GT2 or 3 HCV, therapy with SOF/VEL was again well tolerated with few differences in AEs or SAEs, minus the avoidance of RBV associated toxicities (See Section 1.2.2.2). Patients who received SOF/VEL for either 12 or 24 weeks with decompensated cirrhosis experienced AEs and SAEs typical for patients with decompensated cirrhosis in no pattern that could be attributed to study drug. Patients with decompensated cirrhosis who received SOF/VEL + RBV for 12 weeks also experienced AEs and SAEs consistent with underlying liver disease as well as toxicities expected with RBV treatment.

In summary, there is currently no approved treatment for patients with recurrent HCV posttransplantation. Treatment during the time period prior to re-infection may be unique and mimics that of acute infection, as the nidus of HCV chronic infection (pretransplant liver) has been removed. Thus this may offer an opportunity for a short course of therapy (eg, 4 weeks), to be successful. If high rates of SVR can be obtained with a short, IFN-free, RBV-free, pangenotypic regimen in the peri-operative period, this would render the patient's new liver graft free from HCV and the sequelae of events towards end stage liver disease post transplantation could be avoided.

During the conduct of this study, the sponsor together with the investigator will perform ongoing safety review.

#### **1.10. Compliance**

This study will be conducted in compliance with this protocol, Good Clinical Practice (GCP), and all applicable regulatory requirements.

## 2. OBJECTIVES

The primary objectives of this study are:

- To explore the antiviral efficacy of treatment with SOF/VEL FDC therapy administered for four weeks following liver transplantation as measured by sustained virologic response 12 weeks after cessation of treatment (SVR12)
- To evaluate the safety and tolerability of SOF/VEL in HCV-infected subjects in the peri-operative and post-transplant period

The secondary objectives of this study are:

- To determine the percentage of subjects who attain SVR at 4 weeks after cessation of treatment (SVR4)
- To evaluate the proportion of subjects with virologic failure
- To assess rates of graft survival, graft function, acute rejection and immunosuppressive therapy during treatment with SOF/VEL
- To evaluate the emergence of viral resistance to SOF and VEL during treatment and after cessation of treatment
- To evaluate the kinetics of circulating HCV RNA during treatment and after cessation of treatment
- To characterize pharmacokinetics of SOF/VEL

The exploratory objectives of this study are:

PPD

### **3. STUDY DESIGN**

#### **3.1. Endpoints**

The primary endpoint of this study is:

- The primary efficacy endpoint is SVR12 (HCV RNA < lower limit of quantification [LLOQ] 12 weeks after the date of last dose of study drug) for subjects in the Full Analysis Set.

The secondary endpoint of this study is:

- The proportion of subjects with HCV RNA < LLOQ at 4 weeks after cessation of treatment (SVR4)
- The proportion of subjects with HCV RNA < LLOQ on treatment
- The proportion of subjects with virologic failure (defined as HCV RNA  $\geq$  LLOQ at end of treatment or relapse during Post-treatment follow-up)

#### **3.2. Study Design**

This is an open-label study that will evaluate the safety, tolerability and antiviral efficacy of SOF/VEL administered for 4 weeks in HCV-infected adult male and female subjects who are undergoing liver transplantation.

HCV RNA will be assessed at each visit.

#### **3.3. Study Treatments**

For all subjects SOF/VEL tablet (400 mg/100 mg) once daily will be started the day of the subject's liver transplant if the transplant is completed before noon and the following day if it is completed after noon and will continue for 4 weeks. The planned first dose may be delayed for up to 1 day if, in the investigators opinion, delay is in the subject's medical interest. The subject will receive 4 weeks of study drug.

#### **3.4. Visit Schedule**

All subjects will complete the following study visits: Screening; Pre-surgery (if needed); On-Treatment visits Days 1, 3, 5, 7, 14, 21, and 28; and Post-treatment Visits at Weeks 1, 2, 4, and 12 following the last dose of study drug.

Screening assessments will be completed at the time a subject is identified as a potential study participant to give sufficient time for the subject to provide informed consent and perform screening assessments. Subject's screening data will be confirmed in the pre-operative period (within 48 hours of the planned transplant) at the Pre-surgery visit if the screening visit occurs more than 48 hours before the liver transplant surgery is started.

If a separate informed consent is signed, samples of the explanted liver will be taken during surgery.

The assessments performed at each visit are described in Section 6 and Appendix 2.

### **3.5. Discontinuation Criteria**

When medically feasible, the Medical Monitor must be consulted prior to subject discontinuation.

Study drug must be discontinued in the following instances:

- Unacceptable toxicity, as defined in Section 7.6 of the protocol, or toxicity that, in the judgment of the investigator, compromises the ability to continue study-specific procedures or is considered to not be in the subject's best interest
- If a subject experiences graft dysfunction (including primary graft non-function) requiring relisting for liver transplant, treatment will be stopped
- If subject is relisted for transplantation for any reason treatment will be stopped
- Subject receives a 2nd liver transplant while on study treatment
- Pregnancy of female subject
- Significant protocol violation
- Subject request to discontinue for any reason; it is important to determine whether the withdrawal of consent is primarily due to an AE, lack of efficacy, or other reason
- Discontinuation of the study at the request of Gilead, regulatory agency, or an Institutional Review Board (IRB)/Independent Ethics Committee (IEC)

If a subject meets discontinuation criteria during treatment, an Early Termination visit will be required (Section 6.4) Subjects who permanently discontinue all study drugs for any reason including safety and/or tolerability concerns prior to completion of the assigned dosing period will be followed according to the Post-treatment study assessments to determine whether the subject achieves SVR.

### **3.6. Subject Stopping Rules**

The Gilead Medical Monitor must be consulted prior to discontinuation of study drug unless the investigator believes that immediate action is warranted to ensure the continued safety of the subject.

Administration of study medication may be discontinued due to a clinical or laboratory event. There is no option for SOF/VEL dose reduction. If SOF/VEL is stopped due to toxicity, it must

not be restarted and the subject must complete an ET visit. Any interruptions of study medication must be discussed with the Sponsor Medical Monitor prior to restarting.

Subjects who meet any of the following laboratory or medical criteria must stop all study medication(s):

- Any medical condition (in the opinion of the Medical Monitor) for which the risks of treatment outweigh the benefits
- Commencement of dialysis
- Any Grade 3 or greater rash associated with constitutional symptoms
- Any Grade 4 adverse event assessed as related to SOF/VEL

### **3.7. End of Study**

Subjects are considered to have completed the study after the Post-treatment Week 12 follow-up visit, regardless of treatment duration, unless the subject early terminates because HCV RNA is  $\geq$  LLOQ. If the subject terminates early due to HCV RNA  $\geq$  LLOQ, the subject will complete the post treatment Week 4 visit as their final visit.

### **3.8. Substudies**

#### **3.8.1. Optional Archive Sample**

PPD

PPD

## **4. SUBJECT POPULATION**

### **4.1. Number of Subjects and Subject Selection**

Approximately 10 subjects with chronic HCV awaiting liver transplantation will be enrolled.

In order to manage the total study enrollment, Gilead Sciences, Inc. at its sole discretion, may suspend screening and/or discontinue the enrollment at any site at any time (upon written notice to the site). Discontinuation of the enrollment phase may result in the immediate ineligibility of all subjects screened but not yet enrolled, regardless of the progress or outcome of the screening assessments performed.

### **4.2. Inclusion Criteria**

Subjects must meet all of the following inclusion criteria to be eligible for participation in this study.

- 1) Willing and able to provide written informed consent or for those subjects where hepatic encephalopathy affects their ability to provide initial or ongoing consent, has an appropriate and legally-authorized representative (LAR) willing and able to provide consent on behalf of the subject.
- 2) Male or female, age  $\geq 18$  years
- 3) HCV RNA infection with quantifiable virus at Screening or documented in the patient's medical record.
- 4) Chronic HCV infection ( $\geq 6$  months) as documented by either prior medical history or liver biopsy
- 5) Currently on the liver transplantation wait list (both transplant from deceased or living donor will be considered acceptable)
- 6) Screening ECG without clinically significant abnormalities.
- 7) A negative serum pregnancy test is required for female subjects (unless surgically sterile or greater than two years post-menopausal; see [Appendix 4](#) for definitions).
- 8) Male subjects and female subjects of childbearing potential who engage in heterosexual intercourse must agree to use protocol specified method(s) of contraception as described in [Appendix 4](#).
- 9) Male subjects must agree and refrain from sperm donation from the date of screening until at least 30 days after the last dose of study drug.
- 10) Lactating females must agree to discontinue nursing before the study drug is administered.

- 11) Subject must be able to comply with the dosing instructions for study drug administration and be able to complete the study schedule of assessments, including all required Post-treatment visits.

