#### **4.3. Exclusion Criteria**

Subjects who meet *any* of the following exclusion criteria are not to be enrolled in this study.

- 1) Receipt of an HCV infected liver
- 2) Any serious or active medical or psychiatric illness which, in the opinion of the investigator, would interfere with subject treatment, assessment, or compliance
- 3) HIV infection or a positive hepatitis B virus surface antigen result
- 4) Current malignancy (with exception of HCC within local listing criteria, certain resolved skin cancers or other early cancer for which surgical resection is considered to be completely curative)
- 5) Treatment with any approved or experimental medication with known anti-HCV activity within 1 month prior to screening date
- 6) Prior exposure to a HCV NS5B nucleotide/side inhibitor including SOF or to an HCV NS5A inhibitor
- 7) Patients on hemodialysis prior to or at the time of transplantation will be excluded
- 8) Participation in a clinical study with an investigational drug or biologic within 28 days prior to screening visit, unless information on the investigational drug is available to indicate that there is no potential drug interaction (safety or efficacy)
- 9) Use of any prohibited concomitant medications as described in Section 5.3. Known hypersensitivity to the SOF, VEL, the metabolites, or formulation excipient.

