## 5.3. Prior and Concomitant Medications

Concomitant medications taken within 30 days prior to Screening, up to and including 30 days after the last dose of study need to be recorded in the source documents and eCRFs.

The following medications are prohibited from **28 days prior to the Day 1** visit through the end of treatment:

- Investigational agents or devices for any indication

Concomitant use of certain medications or herbal/natural supplements (such as substrates, inhibitors or inducers of drug transporters or metabolizing enzymes, eg, P-gp or CYP3A) with the study drug may result in pharmacokinetic interactions resulting in increases or decreases in exposure of the study drug or these medications.

[Table 5-1](#) below contains medications that are prohibited from **21 days prior to Day 1** through the end of treatment and those medications that may be used with caution. The use of amiodarone is prohibited from **60 days prior to Day 1** through the end of treatment.

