### **6.1. Subject Enrollment and Treatment Assignment**

### **6.2. Pretreatment Assessments**

#### **6.2.1. Screening Visit/Pre-Surgery**

Subjects will be initially screened to determine their eligibility for participation in the study (they are required to be on the waitlist for liver transplantation). If the screening visit occurs more than 48 hours before the liver transplant surgery is started, the subject will also be reassessed within 48 hours of transplantation to determine their continued eligibility at the pre-surgery visit.

Screening period is the time from initial screen (ie, identification of the subject as being on the liver transplant waitlist and potentially meeting inclusion/exclusion criteria for the study) until administration of the first dose of study treatment.

From the time of obtaining informed consent through the first administration of investigational medicinal product, record all serious adverse events (SAEs), as well as any adverse events related to protocol-mandated procedures on the adverse events case report form (eCRF). All other untoward medical occurrences observed during the screening period, including exacerbation or changes in medical history are to be captured on the medical history eCRF. See [Section 7 Adverse Events and Toxicity Management](#) for additional details.

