### 6.9.2. Medical History

Medical history including details regarding illnesses and allergies, date(s) of onset, and whether condition(s) is currently ongoing, and medication history will be collected on all subjects during screening up to the day of dosing. This will include information regarding the subject's HCV treatment history.

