### **8.2.1. Analysis Sets**

#### **8.2.1.1. Efficacy**

The analysis set for antiviral activity analyses will be the FAS which includes subjects who were enrolled into the study, received a liver transplant while on study, and took at least one dose of study drug.

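### Does the plan need a separate SVR12 row for subjects whose HCV RNA was already below LLOQ at transplant?

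*Protocol*

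**What the plan says.** Inclusion criterion 3 (Protocol 4.2) is met by "HCV RNA infection with quantifiable virus at Screening or documented in the" patient's medical record. The record needs no date. Criterion 4 asks for chronic infection of at least six months, shown by history or biopsy.

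Protocol 4.3 excludes "Treatment with any approved or experimental medication with known anti-HCV activity within 1 month prior to screening date", which counts back from screening and not from transplant. It also excludes "Prior exposure to a HCV NS5B nucleotide/side inhibitor including SOF or to an HCV NS5A inhibitor". Protocol 5.3 bars investigational agents from 28 days before Day 1.

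Where screening is more than 48 hours before surgery, Protocol 6.2.1 says "the subject will also be reassessed within 48 hours of transplantation to determine their continued eligibility at the pre-surgery visit". HCV RNA is drawn at that visit (Appendix 2), but no level is set for it. Under Protocol 6.9.2, "medication history will be collected on all subjects during screening up to the day of dosing", including HCV treatment history. Footnote e of Appendix 2 adds an HCV RNA sample immediately before transplant.

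The efficacy set (Protocol 8.2.1.1) is enrolled subjects who "received a liver transplant while on study, and took at least one dose of study drug". SAP 3.1.2 agrees. SAP 6.1.1 defines SVR12 as HCV RNA below 15 IU/mL twelve weeks after treatment, with no condition on RNA at transplant.

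**The concern.** Protocol 1.8 describes post-transplant recurrence in patients with detectable HCV RNA before surgery. A subject who has already cleared the virus may reach SVR12 whatever the four-week course does. With about 10 subjects, each one carries 10 percentage points of the primary estimate.

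The entry text does not close the door. An old record can satisfy criterion 3, the washout runs from screening although the wait for an organ is variable (SAP 1.2), and the pre-surgery recheck has no RNA threshold. The planned summaries do not obviously compensate. The only categorical split of pretransplant RNA is at 800,000 IU/mL, the SVR12 subgroups in SAP 3.4 do not include RNA, and SAP baseline is the last value up to the first dose, normally after transplant, when RNA has already fallen. It would seem natural to ask for a count of subjects below LLOQ before transplant and an SVR12 figure without them.

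**Working it through.** **The plan's own figure.** Inputs are n = 10 and a two-sided 95% Clopper-Pearson interval (Protocol 8.5.1 and 8.8; SAP 1.3 and 6.1.3). The limits are L = Beta⁻¹(0.025; x, n−x+1) and U = Beta⁻¹(0.975; x+1, n−x). The widest case is x = 5: 18.7% to 81.3%, length 62.6 points. This reproduces the stated maximum of 63%.

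**Largest bias.** Let k be the number of FAS subjects below LLOQ at transplant (not given in the documents), all assumed to count as SVR12. Let p be the assumed SVR12 rate in the others. Then

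bias = [k + (10 − k)p]/10 − p = k(1 − p)/10.

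For k = 1: p = 0.9 gives 0.01, p = 0.7 gives 0.03, p = 0.5 gives 0.05.

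**Effect of removing one assumed success (k = 1).**

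| All FAS (95% CI) | Without that subject (95% CI) | Fall in estimate | Fall in lower limit |
|---|---|---|---|
| 10/10 = 100% (69.2–100) | 9/9 = 100% (66.4–100) | 0 points | 2.8 points |
| 9/10 = 90.0% (55.5–99.7) | 8/9 = 88.9% (51.8–99.7) | 1.1 points | 3.7 points |
| 8/10 = 80.0% (44.4–97.5) | 7/9 = 77.8% (40.0–97.2) | 2.2 points | 4.4 points |

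For k = 2, 9/10 becomes 7/8 = 87.5% (47.3–99.7) and 8/10 becomes 6/8 = 75.0% (34.9–96.8). For k = 0 nothing moves.

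**How such a subject could arise.**

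- *Cleared by treatment that ended more than a month before screening.* Exclusion 6 removes regimens containing an NS5B nucleos(t)ide or NS5A inhibitor. For the rest, SAP 5.1 lists only peginterferon with or without ribavirin as the last regimen. It lists only non-response, relapse or breakthrough, and early discontinuation as the response. SAP 3.1.2 speaks of all enrolled subjects as already transplanted and dosed, so these categories were probably written with the cohort known.
- *Cleared by treatment between screening and transplant.* Exclusion 6 applies again at the pre-surgery recheck, investigational agents are barred, and treatment history is taken up to dosing.
- *Spontaneous clearance.* Criterion 4 requires chronic infection, and the documents give no reason to expect clearance.

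**Would planned output show it?** SAP 5.1 summarises pretransplant HCV RNA as a continuous variable, including the minimum. SAP 3.7 sets every value below LLOQ, including target not detected, to 14 IU/mL. A minimum of 15 IU/mL or more means k = 0 at the sample used; a minimum of 14 means k is at least 1. On the log scale these are log₁₀ 14 = 1.146 and log₁₀ 15 = 1.176, which still differ at one decimal (1.1 against 1.2). Listing 21 then gives RNA by visit for each FAS subject, and Protocol 8.3 puts the reported values in that listing. With about 10 people, a reader can count k and recompute SVR12 by hand.

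**The case for a change.** The best case for a change is that it is nearly free: one count and one row in SAP Table 9, from samples already taken. If k = 0, one line closes the question; if not, readers of a ten-subject estimate need to know. The prior-treatment subgroup is only a partial proxy because it misses spontaneous clearance. The evidence that k = 0 is indirect, since the response categories describe treated subjects only and early discontinuation is not strictly failure. SAP 5.1 also does not say which sample is the pretransplant one. If it were the screening sample, the minimum would miss someone who cleared while waiting.

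Part of this stands. No criterion requires quantifiable RNA at transplant, and the pretransplant sample is undefined. But SAP 5.1 lists pretransplant and baseline HCV RNA as separate variables, so the post-surgical value is not meant. The sample drawn just before surgery is the obvious choice, and Listing 21 covers all visits whichever is summarised.

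The suggested row also has a fault. Protocol 1.8 refers to detectable RNA, whereas the row would cut at LLOQ. SAP 3.7 separates RNA detected below LLOQ from target not detected. A subject in the first group belongs to the population the rationale describes, yet the row would drop that subject. It would also be specified after dosing, and with one subject removed the maximum interval length rises from 62.6 to 65.1 points.

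**Conclusion.** No change is needed. The gap in the eligibility text is real, but the route through it is narrow and probably empty, and the planned summaries and listings would expose anyone who took it. The undefined pretransplant sample is a gap that analysts can fill sensibly. If a subject with target not detected before transplant did appear, ordinary reporting could describe that subject, and SAP 1 already provides for documenting later additions in the CSR.

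The study is exploratory and tests no hypothesis (SAP 6.1.2), so no error rate is at stake. One such subject would inflate SVR12 by at most 1 to 5 points for p from 0.9 down to 0.5, well inside the interval. This rests on 10 FAS subjects, on assumed values of k and p, and on every aviremic subject counting as a success. That k is probably zero is an inference from the exclusions and the SAP's treatment categories, not a reported result. An extra row would most likely duplicate the FAS figure.
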